8.3.1 Aim

To confirm the domain structure, reliability, validity, responsiveness and minimally important differences of the PROM in the context of short-term surgical outcomes up to 6 months post-surgery.

8.3.2 Method

Postal/online survey based upon patient preferences.

8.3.3 Sample and Sample Size

To achieve a minimum new sample of **300** women required for our confirmatory factor analysis (CFA)⁴⁴, and in anticipation of a response rate of around 70%, we will administer our survey to at least 430 women. Based on the frequency of the different interventions in the NHS (see page 4), the sample will include:

- **150 (215 approached)** women having surgery for POP. Currently, mesh is only used in abdominal procedures. This means we expect to recruit 10 women who are having abdominal mesh and 140 women having alternative surgery.
- **100 (143 approached)** women having surgery for SUI, none of which will be with mesh, because this procedure is not currently being conducted.
- **50 (72 approached)** women having mesh complication surgery.

We will undertake an analysis of the communalities and the number of items per factor to confirm the adequacy of the sample size as per Survey 3a.⁴³ These sample sizes are also adequate to meet the thresholds for the responsiveness and minimally important difference analysis reported below.⁴⁵

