5.6 Setting/Context

NHS secondary care urogynaecology services (Groups 1 and 2) and the Sheffield Mesh Removal Centre (Group 3).

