5.7 Recruitment and Consent

Our core recruitment centres include ethnically and geographically diverse populations (inner city, coastal, rural) across, Sheffield, Norfolk, Surrey and London. Approximately 200-300 women per year undergo POP surgery in each centre (up to 1200 women in total per year), and 50 women per year undergo surgery for SUI (up to 200 in total per year). Approximately 50 women per year undergo mesh removal at the Sheffield Mesh Removal Centre. Clinical team members will act as patient identification centres and facilitate recruitment of women with different characteristics using existing databases of operation notes and approaching women attending for outpatient appointments post-surgery. We also have access to a further 21 UK-wide secondary care urogynaecology units via the The British Society of Urogynaecology Research Network (BSUG RN) who will support recruitment to ensure sample diversity. All participant facing materials will be co-developed with PPI input and written in plain English language with a Flesch reading age of 11 years old.

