7.3.4 Data Analysis

Each reviewer will be asked to provide recommendations on the suitability of the original text for translation and, in instances where translation may prove challenging, is invited to suggest modifications to the original text to improve ease of translation. Recommendations from all translators will be fed back to the project team who will consider recommendations and make alterations to the original text accordingly during a project team meeting. We will invite a subset (n=12) of our original interviewees in the UK from exercise 2b to take part in a second round of cognitive debriefing interviews to comment on the resulting questionnaire suggested from the translatability assessment to confirm that any adjustments made are acceptable and meaningful to patients. New patients may also need to be recruited though depending on the response rate for this activity.

7.4 Outcomes from Work Package 2

The outcomes will be a concept elaboration document and a prototype long-form PROM with an initial pool of items and domains that has been reviewed by stakeholders and patients, checked for minor modifications between the modes of administration, has face validity and is easily translatable. The next stage will be to evaluate the psychometric properties of the initial item pool which will be undertaken in WP3.

8. WP3 (Months 19-34)

To establish the PROMs psychometric properties we will undertake one survey to reduce its item number and identify its domain structure (3a) and a second survey with a new sample of women to confirm its domain structure, reliability, validity, and responsiveness in the context of short-term surgical outcomes (3b).

8.1 Survey (3a): To Reduce the Number of Items and Identify the Domains and Scoring Algorithms of the PROM (Months 19-22)

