8.3.4 Data Collection

Women will complete the PROM before surgery, and then at 3 months and 6 months post-surgery, along with other selected instruments identified in WP1. To assess test-retest reliability, a subsample of women in each group will be asked to complete the PROM at two time points one week apart before surgery. To establish test-retest reliability women will complete the PROM twice, one week apart. The exact time is to be confirmed but is anticipated a week after the completion of the 3-month post-surgery PROM when patients are more likely to be stable and there is time in the study to collect this data rather than 1 week post 6-month completion.

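### Survey 3b's target of 50 mesh-complication women measured before and after surgery cannot be supplied by the one Group 3 centre the protocol names

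*Protocol*

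**What the plan says.** Section 8.3.3 sets the survey 3b sample: "To achieve a minimum new sample of 300 women required for our confirmatory factor analysis (CFA"), with the number approached inflated "in anticipation of a response rate of around 70" per cent. It splits the 300 into 150 prolapse (POP), 100 stress incontinence (SUI) and, for Group 3, "50 (72 approached) women having mesh complication surgery". It adds that these sizes also suffice for the responsiveness and minimally important difference (MID) analyses.

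Section 8.3.4 gives the schedule: "Women will complete the PROM before surgery, and then at 3 months and 6 months post-surgery".

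On supply, section 5.6 names the settings as "NHS secondary care urogynaecology services (Groups 1 and 2) and the Sheffield Mesh Removal Centre (Group 3"). Section 5.7 gives the volume: "Approximately 50 women per year undergo mesh removal at the Sheffield Mesh Removal Centre". For SUI it gives, per core centre, "50 women per year undergo surgery for SUI (up to 200 in total per year"), and for POP 200-300 per centre and up to 1200 in total. Section 5.7 and the abstract also say that 21 further units of the urogynaecology research network will help to recruit, but no operation volumes are given for them.

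On timing, the work package is headed "8. WP3 (Months 19-34"). Survey 3a occupies months 19-22, and section 8.2 says that the final version it produces is what 3b tests. Months 35-36 are kept for dissemination, writing up and archiving.

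**The concern.** Survey 3b is prospective. A woman counts fully only if she is found before her operation, completes the final questionnaire then, and is followed for 6 months. Surveys 3a and 4a can draw on women operated on in the past; 3b cannot. Its Group 3 sample is therefore capped by the number of operations that fall in a short window at a centre with a stated annual volume.

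Section 3 says that no questionnaire has been designed specifically for women having surgery for mesh complications, so this group is a main reason for the study. If the stated 50 cannot be reached, the 150/100/50 composition in 8.3.3 is not what the survey will deliver. The adequacy statement in that section then rests on group sizes that will not exist, and the test-retest subsample that 8.3.4 wants in each group has to come from a much smaller Group 3.

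**Working it through.** **The plan's own figures.** Number approached = target / 0.70, rounded up: 150/0.70 = 215, 100/0.70 = 143, 50/0.70 = 72. The sum is 430, as stated. The inflation is correct; the question is supply.

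**Window.** The start is month 23, after 3a ends in month 22. This agrees with section 9.3, which has WP5 (months 23-34) running concurrently with 3b. For a 6-month form by month 34, the last operation is in month 34 - 6 = 28. Months 23-28 are 6 months of operations, with no time left for analysis inside WP3.

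**Group 3 supply.** Operations = 50 x months/12; respondents = 0.70 x operations.

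| Operations in months | Follow-up possible by month 34 | Operations | Respondents at 70% |
|---|---|---|---|
| 23-28 (6 months) | 3 and 6 months | 25 | 17.5 |
| 23-31 (9 months, cumulative) | at least 3 months | 37.5 | 26 |
| 23-34 (12 months, cumulative) | baseline at least | 50 | 35 |
| 19-34 (all 16 months of WP3, partly before the final version exists) | mixed | 66.7 | 46.7 |

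Against the 6-month window, the target of 50 is 50/25 = 2.0 times the operations performed, and the 72 to approach is 72/25 = 2.9 times. Approaching 72 takes 72/50 x 12 = 17.3 months. Doing it in 6 months would need 72 x 12/6 = 144 operations a year. No window inside WP3 supplies 72 women to approach, or 50 respondents at 70%. The 70% is a response rate; the plan makes no separate allowance for loss between baseline and 6 months.

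**Total under the stated split.** With the POP and SUI quotas filled: 150 + 100 + 17.5 = 267.5, about 267 against 300.

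**SUI at the core centres alone.** 200 x 6/12 = 100 operations against 143 to approach.

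**Room in POP.** Four core centres at 200-300 a year give 800-1200, so 400-600 operations in 6 months. Keeping 300 with 100 SUI and 17 Group 3 women needs 300 - 117 = 183 POP women, or 183/0.70 = 262 approached, which fits within 400.

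**The case against.** The window is inferred. Section 8.3 gives no recruitment months, and the timetable cells cannot be read in the text available. This matters for the figure of 25 but not for the conclusion, because the longest window after 3a still yields only 50 women to approach, with no follow-up for the latest of them.

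Supply may be larger than stated. Section 5.7 counts mesh removals, whereas Group 3 in section 5.3 is surgery for mesh complications, which may be wider. Section 12.3 describes the team as one key centre in the mesh removal service, so others may exist, and the 21 network units may add cases. All this is possible, but the protocol gives no volume for any of it, and section 5.6 assigns Group 3 to Sheffield alone.

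Three stronger readings are tempting and are not supported:

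- *That 300 is out of reach.* It fails only under the 150/100/50 split, since POP has ample surplus. Section 8.3.3 also ties the 300 to the factor analysis, and nothing says that this analysis needs 6-month completers; baseline forms could serve.
- *That SUI also fails, giving about 150 + 70 + 17.5 = 237 in all.* This counts core centres only. The gap is 143 - 100 = 43 women to approach, about 2 for each of the 21 further units. The documents do not show that these units cannot supply them, nor that they can.
- *That a Group 3 responsiveness or MID result loses a calculable amount of precision.* Sections 8.3.5 and 8.4 describe these analyses for the questionnaire as a whole and promise no Group 3 estimate.

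**Conclusion.** The stated Group 3 size in survey 3b is not deliverable from the stated source. On the protocol's own volume and response rate, about 17-18 women would have both pre-surgery and 6-month data, against 50 planned. About 26 would have baseline data if operations to month 31 are included, and 35 if operations to month 34 are. The planned split then totals about 267.

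This rests on about 50 operations a year, Sheffield as the sole Group 3 source, a 70% response, a start at month 23 and no loss to follow-up. The exact count depends on the inferred window; the shortfall does not. The point is confined to Group 3 and to the composition of the sample. It does not show that the total of 300, the SUI quota or the pooled analyses must fail.

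**What to change.** In 8.3.3, restate the Group 3 target as about 17-18 women with 6-month data, adding about 26 with baseline data if operations to month 31 are included, or up to 35 to month 34. State the recruitment window that these figures assume. Move the unfilled places to POP so that the factor analysis total stays at 300. Limit the statement that the sample sizes are adequate for responsiveness and MID to the pooled sample. Report any Group 3 estimate with its confidence interval, and do not describe it as established.

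Alternatively, if other units or a wider set of mesh-complication procedures are meant to supply Group 3, amend 5.6 and 5.7 to name them with their annual volumes, and show that these reach 72 in the window. Volumes for the network units would settle the SUI question at the same time.

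The cost is protocol wording, a smaller stated Group 3 figure and a sample weighted more towards POP. The total number of women does not rise. The change is best made before 3b starts.

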8.3.4 Data Collection

Women will complete the PROM before surgery, and then at 3 months and 6 months post-surgery, along with other selected instruments identified in WP1. To assess test-retest reliability, a subsample of women in each group will be asked to complete the PROM at two time points one week apart before surgery. To establish test-retest reliability women will complete the PROM twice, one week apart. The exact time is to be confirmed but is anticipated a week after the completion of the 3-month post-surgery PROM when patients are more likely to be stable and there is time in the study to collect this data rather than 1 week post 6-month completion.

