8.3.5 Psychometric Analysis

We will undertake a number of psychometric analyses consistent with best practice for developing robust PROMs.³⁻⁶ The tests will include assessing levels of missing data and response patterns, CFA, internal consistency reliability, test-retest reliability and construct validity including known groups validity and convergent validity. It has been reported that scale validity is supported if at least two different forms of construct validity have been assessed.⁴⁶ Known groups validity will be examined by testing a priori hypotheses pertaining to comparisons of the PROM scores between subgroups of patients defined by their surgical, demographic and other clinical characteristics (e.g., POP, or SUI). Convergent validity will be assessed by comparing the results of our PROM with other similar measures (selected following our work in WP1). To assess the PROMs responsiveness, four different statistical distribution-based methods will be used including: i. effect size, ii. standardised response means, iii. significance of change, and the iv. responsiveness statistic comparing the findings across all three time points. Minimally important differences will be calculated using an anchor-based method along with a priori hypotheses and receiver operating characteristic (ROC) curves to identify important changes in the new PROM that discriminate between participants who self-report as having improved vs. not-improved as recommended by the COSMIN guidelines.^{5,47} Finally, we will use a MIMIC model to check that there is no construct bias in the PROM.

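### Section 8.3.4 describes the survey 3b test-retest in two ways, differing in occasion and in who is retested, and does not say which one supplies the reported reliability

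*Protocol*

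**What the plan says.** Survey 3b has three main assessments (8.3.4): "Women will complete the PROM before surgery, and then at 3 months and 6 months post-surgery". The same paragraph then describes the retest in consecutive sentences.

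- Plan A: "a subsample of women in each group will be asked to complete the PROM at two time points one week apart before surgery". The size of the subsample is not given.
- Plan B: "To establish test-retest reliability women will complete the PROM twice, one week apart". No subsample is named. On timing: "The exact time is to be confirmed but is anticipated a week after the completion of the 3-month post-surgery PROM". The reason offered is that this is "when patients are more likely to be stable and there is time in the study to collect this data", set against a retest a week after the 6-month form.

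The aim in 8.3.1 is to confirm, among other properties, "reliability, validity, responsiveness and minimally important differences of the PROM in the context of short-term surgical outcomes up to 6 months post-surgery". Section 8.3.5 (Psychometric Analysis) lists test-retest reliability without naming an occasion. Section 8.4 claims reliability as established for outcomes up to 6 months after treatment. Survey 4a, by contrast, has a single retest plan (9.1.4).

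**The concern.** The two plans collect different data. Plan A retests women awaiting surgery, and plan B retests women about three months after it. Plan A takes a subsample of each group, while plan B names no restriction. Nothing says that both will be run or which one is primary.

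This affects the result because an ICC describes an instrument in a population on an occasion. With the same measurement error, it rises or falls with the spread of true scores between women, and that spread need not be the same before surgery as three months after. Only plan B falls inside the period named in the aim.

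Stability over the week is an expectation in the text. The self-reported improved or not-improved rating in 8.3.5 is named for the minimally important difference, not for the retest. If the retest form carries no question about change, women who changed cannot be identified afterwards.

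All of this concerns which forms go to whom and when. An analysis plan cannot supply a retest or an item that was not collected.

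**Working it through.** **The plan's own figure.** No number is given for the retest. The survey total does reproduce. At 70% response, 300/0.70 = 428.6, which rounds up to 429 against at least 430 stated. By group, 150/0.70 gives 215, 100/0.70 gives 143 and 50/0.70 gives 72, and 215 + 143 + 72 = 430. The point does not depend on this.

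**The two plans side by side (8.3.4).**

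| | Plan A | Plan B |
|---|---|---|
| Occasion | Before surgery | About a week after the 3-month form, to be confirmed |
| Who | A subsample of each group | Women, no subsample named |
| How many | Not stated | Not stated |
| Within the post-surgery aim of 8.3.1 | No | Yes |

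**Effect of the occasion (assumed values, because no scale exists yet).** ICC = between-woman variance / (between-woman variance + error variance). Take ICC 0.80 on one occasion, so the variances are 0.8 and 0.2. Hold the error at 0.2 and let the between-woman SD on the other occasion be r times as large: ICC = 0.8r² / (0.8r² + 0.2).

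- r = 0.7: 0.392/0.592 = 0.66
- r = 0.8: 0.512/0.712 = 0.72
- r = 1.2: 1.152/1.352 = 0.85

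The direction is not known in advance. Women all selected for surgery may be more alike than a 3-month mix of improved and unimproved women. Equally, scores bunched at the good end after successful surgery may narrow the 3-month spread.

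**Effect of unrecognised change (assumed).** Suppose true change over the week differs between women with variance v, expressed as a fraction of total score variance and independent of the starting score. It adds v/2 to the average variance of the two occasions: ICC = 0.8/(1 + v/2).

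- v = 0.1: 0.8/1.05 = 0.76
- v = 0.2: 0.8/1.10 = 0.73
- v = 0.4: 0.8/1.20 = 0.67

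**Effect of the number retested.** Approximate 95% limits for an ICC of 0.80 come from tanh(atanh(0.80) ± 1.96/√(n − 1.5)).

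- n = 50 (an assumed subsample): 0.67 to 0.88
- n = 300 (the whole sample retested, an upper bound): 0.76 to 0.84

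The unstated subsample size therefore leaves the precision open as well.

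**The case against.** The strongest reply is that the paragraph has a natural reading. It calls the timing provisional, names the 3-month occasion as anticipated and gives reasons for it, so the pre-surgery sentence may simply be left over. Alternatively, both retests may be intended. A pre-surgery retest is not irrelevant either, since the pre-surgery form is one of the three assessments. This stands in part: use of an occasion outside the aim is a risk, not a certainty. But the text states neither reading, and the two readings lead to different data collection.

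It can also be said that the selection of stable women belongs in an analysis plan. The selection rule may well be there. The question on the form, however, has to exist before the forms are sent.

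Several stronger inferences are tempting, and the protocol does not support them.

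- **Sites following different sentences and two populations being pooled by accident.** Survey 3b is postal or online (8.3.2). University-based staff run the study day to day (section 17), and NHS time is for identifying patients and obtaining consent to contact (20.1). One central team would set the schedule.
- **A distorted responsiveness statistic.** Section 8.3.5 names a "responsiveness statistic comparing the findings across all three time points" but gives no denominator and does not say that retest data enter it.
- **A minimally important difference smaller than measurement error that nobody checks.** The standard error of measurement, the smallest detectable change and their comparison with the minimally important difference may sit in an analysis plan that is not shown.
- **The same instrument passing on one occasion and failing on the other at 0.70.** The protocol sets no such threshold.

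**Conclusion.** The contradiction stands and is confined to one paragraph: 8.3.4 gives two retest plans that differ in occasion and in who is retested, and no other section settles which applies. The 3-month occasion is the one that matches the aim in 8.3.1, and it is the one for which the protocol offers a stability rationale, although that rationale is argued against 6 months and not against pre-surgery.

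The size is illustrative. Assuming ICC 0.80 on one occasion and equal measurement error on both, a spread 0.7 to 1.2 times as large on the other gives 0.66 to 0.85. This shows that the choice can matter in either direction; it does not predict how this PROM will behave. Confidence is high for the conflict in the text. It is lower for the stability point, part of which may be covered in an analysis plan. The correction should be made before retest forms go out.

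**What to change.** In 8.3.4:

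1. Make one retest primary, about a week after the 3-month post-surgery form.
2. Delete the pre-surgery sentence, or keep that retest as secondary, reported separately and not pooled with the primary one.
3. State who is retested (all 3-month responders or a subsample of each group) and how many.
4. Add one item to the retest form asking whether anything has changed since the woman last completed it, so that reliability can be estimated in women reporting no change.

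The cost is a change of protocol wording, one extra question, slightly fewer pairs in the stable-women estimate, and some additional forms and follow-up if only a subsample had been planned.

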8.3.5 Psychometric Analysis

We will undertake a number of psychometric analyses consistent with best practice for developing robust PROMs.³⁻⁶ The tests will include assessing levels of missing data and response patterns, CFA, internal consistency reliability, test-retest reliability and construct validity including known groups validity and convergent validity. It has been reported that scale validity is supported if at least two different forms of construct validity have been assessed.⁴⁶ Known groups validity will be examined by testing a priori hypotheses pertaining to comparisons of the PROM scores between subgroups of patients defined by their surgical, demographic and other clinical characteristics (e.g., POP, or SUI). Convergent validity will be assessed by comparing the results of our PROM with other similar measures (selected following our work in WP1). To assess the PROMs responsiveness, four different statistical distribution-based methods will be used including: i. effect size, ii. standardised response means, iii. significance of change, and the iv. responsiveness statistic comparing the findings across all three time points. Minimally important differences will be calculated using an anchor-based method along with a priori hypotheses and receiver operating characteristic (ROC) curves to identify important changes in the new PROM that discriminate between participants who self-report as having improved vs. not-improved as recommended by the COSMIN guidelines.^{5,47} Finally, we will use a MIMIC model to check that there is no construct bias in the PROM.

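### Responsiveness rests mainly on indices of how much women change, with no change hypotheses tied to it; separately, the improved/not-improved ROC cut overstates the MID if well over half improve

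*Protocol*

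**What the plan says.** Protocol 8.3.5 (Psychometric Analysis, survey 3b) sets out how this property is to be assessed: "four different statistical distribution-based methods will be used including: i. effect size, ii. standardised response means, iii. significance of change, and the iv. responsiveness statistic". These are to be set against each other over the three time points. The last of them is not defined.

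On the MID, the same section names an anchor-based approach and hypotheses set in advance, plus the use of "receiver operating characteristic (ROC) curves to identify important changes in the new PROM that discriminate between participants who self-report as having improved vs. not-improved". The contrast is therefore dichotomous. No rule for choosing the cut and no expected proportion improved are given.

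In 8.3.4 the PROM is completed before surgery and at 3 and 6 months, "along with other selected instruments identified in WP1". So comparator change scores will exist at the same waves.

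In 8.3.3 the sample of 300 is set by the confirmatory factor analysis. It is said to be adequate for responsiveness and MID too, by citation and without a calculation.

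Survey 3b is the only source for both properties: 9.1.5 rules them out for survey 4a, and 9.2.6 lists neither for 4b.

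**The concern.** Responsiveness asks whether a change in score follows a real change in the woman. Effect size, SRM and a test of mean change answer another question: how far the average score moved. After an effective operation they can favour a poor instrument, and after an ineffective one they can count against a good instrument. The plan ties no hypothesis about change, and no correlation with change on another measure, to responsiveness. Its a priori hypotheses are attached to the MID.

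For the MID, a cut that best separates improved from not-improved women falls roughly midway between the mean changes of those two groups. If well over half the women improve, both means move up and the midpoint rises above the change that marks the threshold of improvement. Later trials are likely to use this MID for sample size and interpretation. An inflated value gives trials that are too small and causes real benefit to be dismissed.

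**Working it through.** **The plan's own figure.** Number approached = N / 0.70. 300/0.70 = 428.6; 150/0.70 = 214.3, so 215; 100/0.70 = 142.9, so 143; 50/0.70 = 71.4, so 72. The groups sum to 215 + 143 + 72 = 430, as 8.3.3 states. The protocol gives no alpha, power, effect size or improvement rate for responsiveness or MID, so nothing further can be reproduced.

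**Responsiveness.** Inputs: n = 300 complete pairs (8.3.3); two-sided 5% and 80% power (assumed).
- Smallest SRM reaching p < 0.05: 1.96/√300 = 0.113.
- SRM with 80% power: (1.96 + 0.84)/√300 = 2.80/17.32 = 0.16. For groups of 150, 100 and 50 it is 0.23, 0.28 and 0.40.
- Counter-example: 500 simulated samples in which the score's change had no correlation with true change but its mean moved by 0.8 SD. Mean SRM was 0.80, and p < 0.05 in every sample. An instrument that does not follow change at all would pass on SRM and significance.

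**MID from the ROC cut.** Assumptions, none of them in the protocol: true MID 10; SD of PROM change 15; correlation of 0.6 between PROM change and the latent anchor; a woman is improved when the latent anchor exceeds 10; cut maximising sensitivity plus specificity. For proportion improved p, let z = Φ⁻¹(p). The mean change is μ = 10 + 15z. The group means are μ + 0.6×15×φ(z)/p (improved) and μ − 0.6×15×φ(z)/(1−p) (not improved). Their midpoint gives a hand check on the simulated cut.

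| p | μ | improved mean | not-improved mean | midpoint | simulated ROC cut | adjusted logistic |
|---|---|---|---|---|---|---|
| 50% | 10.0 | 17.2 | 2.8 | 10.0 | about 10 | about 10 |
| 60% | 13.8 | 19.6 | 5.1 | 12.4 | about 12.5 | – |
| 70% | 17.9 | 22.3 | 7.4 | 14.9 | about 15 | about 13 |
| 80% | 22.6 | 25.8 | 10.0 | 17.9 | about 18 | about 15 |

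A second parametrisation (true MID 0.50 SD of true change; reliabilities of PROM change and anchor 0.8/0.7 or 0.7/0.5; n = 300) gave cuts of 1.0 times the truth at 50% improved, 1.7 to 2.0 times at 70% and 2.1 to 2.7 times at 80%.

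**Precision.** Under the first set of assumptions at n = 300, the SD of the cut was 3.2 with 50% improved and 3.5 with 80%. It was about 3 to 4 across n = 210 to 300, where 210 = 300 × 0.70 is an assumed loss after baseline. At 80% and n = 300, 1.96 × 3.5 = 6.9, so a single study could return roughly 11 to 25. The adjusted logistic estimate had a quarter to a third of that spread.

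**Consequence for a later trial** (assuming it is sized at 80% power on the estimated MID and the true effect is 10): power = Φ(2.80 × 10/MID − 1.96). With MID 18, Φ(1.56 − 1.96) = 34%. With MID 15, Φ(1.87 − 1.96) = 46%.

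**The case against.** Much can be said for the plan.

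- Significance is one index of four. The documents do not say that responsiveness is decided by a p-value. The responsiveness statistic is undefined and may scale change by variability in stable women, so it cannot be shown that all four indices share the weakness. This stands, and the point is limited to at least three.
- A reader might infer that the MID rests on ROC alone. It does not: an anchor-based method and a priori hypotheses are named in the same sentence. Discrimination against the anchor would itself say something about the validity of change, although it is planned under MID.
- The cut rule and any adjustment could properly sit in an analysis plan that is not shown.
- No improvement rate is stated. The sample mixes prolapse, incontinence and mesh-complication surgery, so one high rate cannot be presumed. The bias is nil at 50% and modest at 60%. The MID part is therefore conditional.
- It is tempting to say the cut is unstable because few women fail to improve. The figures do not support this: its SD is almost the same at 50% and 80% improved. The imprecision comes from the cut-point method and the sample size.
- It is also tempting to say the anchor item is missing from 8.3.4. But 8.3.5 relies on women's self-reported improvement, so collecting it is implied, and the other instruments await WP1.

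What remains is that 8.3.5 itself names the responsiveness methods and ties no test of change validity to them.

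**Conclusion.** The responsiveness point holds on the text. At least three of the four named indices measure amount of change, no hypothesis or change-score correlation is attached to responsiveness, and at 300 complete pairs an SRM of 0.16 is enough for significance with 80% power. Survey 3b offers the only chance to do better, and the data needed are already planned.

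The MID point holds conditionally. If the cut maximises sensitivity plus specificity and well over half the women improve, the MID is overstated: by about half at 70% improved (15 against 10) and by about four fifths at 80% (18 against 10), given SD 15 and anchor correlation 0.6. It is imprecise at any improvement rate. The documents do not establish that most women will improve.

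The adjusted logistic estimate should not be read as a cure. It cuts the excess from 5 to 3 at 70% and from 8 to 5 at 80%, so a bias of about 30% to 50% remains. Its larger gain is in precision. The change is worth making; nothing here invalidates the study.

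**What to change.** In 8.3.5:

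1. Make the main responsiveness evidence a set of hypotheses, with direction and minimum size, on correlations between PROM change and change in the comparators collected before surgery and at 3 and 6 months. Add AUC against the self-rated improvement anchor. Write the hypotheses once WP1 has chosen the comparators and before survey 3b change data are seen. The sample supports this: for r = 0.5 and 300 pairs, the Fisher interval is tanh(0.549 ± 1.96/√297), or 0.41 to 0.58.
2. Report effect size, SRM and significance of change as descriptive only, and define the responsiveness statistic.
3. Make the main anchor-based MID a logistic predictive-modelling estimate adjusted for the proportion improved, with a bootstrap confidence interval. Keep the ROC cut as a sensitivity analysis and state its rule.
4. Report the proportion improved and the anchor–change correlation beside the MID, and state as a limitation that the adjusted estimate remains inflated when well over half improve.

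The cost is revised wording and a little more analysis. No extra participants or survey waves are needed.
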